This section covers only the final analysis. The interim analyses are similar with additional description in Section 18.1. This section is not completely final. More work is needed regarding the details of the approach. Besides, the assumptions need justification.

The primary efficacy analyses are based on a Bayesian cognitive progression model (BCPM). This cognitive progression model incorporates the following aspects:

- Repeated measures for the cognitive endpoint over the recurring 6-month visit schedule, including pre- and post-intervention
- Patient-level random effect
- Proportional treatment effect for slowing of disease progression rate. If there are several active treatment arms, the ISA will describe how this will be modelled.

Let a cognitive endpoint at visit j for research participant i be labelled Y_{ij} , for $j = \dots, -1, 0, 1, 2, \dots$. The reference to negative visits corresponds to cognitive endpoint values from the LCS study, pre-intervention. The Y_{i0} observation corresponds to the baseline visit at the time of the start of intervention. Visits $j=1,2,3$, refer to the post baseline, on treatment visits (each 6-months separated). Within a specific subgroup, the cognitive progression model is

 EPAD - 115736	D2.11 Master Statistical Analysis Plan for the EPAD Platform Proof-of-Concept Trial		
	WP2. Statistical/Methodology Engine Room		Version: v2.0 – Final
	Author(s): [name], [name], [name]		Security: PU

$$Y_{ij} = \begin{cases} \gamma_i + \sum_{v=j}^{-1} \alpha_v + \epsilon_{ij} & j = \dots, -2, -1 \\ \gamma_i + \epsilon_{ij} & j = 0 \\ \gamma_i + \exp(\theta_{t_i}) \sum_{v=1}^j \alpha_v + \epsilon_{ij} & j = 1, 2, 3 \dots \end{cases}$$

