The γ_i , $i=1, \dots, k$, parameters are the random effects specific to a research participant. These random effects represent the mean cognitive total score at the time of treatment (randomization). The α_j parameters represent the change in the mean cognitive score from one visit to the next. The α_j , for $j=0, 1, 2, 3$, are restricted to be negative (decline), representing the mean change from visit $j-1$ to j , restricted to be, on average, negative. For research participant i , the treatment arm is labelled t_i . The cognitive progression rate ratio (CPRR) for treatment T is the parameter $\exp(\theta_T)$. For a control, or placebo treatment, the CPRR is assumed to be 1 ($\theta_T = 0$). Thus, the CPRR parameter for a generic intervention T represents the multiplicative change to the mean decline of a research participant on a control or placebo treatment. If the CPRR is less than 1 then the rate of decline for an intervention T is slower than for a control treatment. The value of the CPRR represents the proportional slowing of the disease. A value of CPRR = 0.75 corresponds to a 25% slowing in the rate of decline and a value of 0.25 represents a 75% slowing in the rate of decline. The errors for the individual observations are modelled as independent normal distributions with a standard deviation of σ . Within each defined subgroup (strata), $g=1, 2, 3, 4$, corresponding to the cognitive status and ApoE4 status ($g=1$ is (+,+), $g=2$ is (+,-), $g=3$ is (-,+), and $g=4$ is (-,+)), a separate set of α 's and σ are modelled (α_g and σ_g). In the primary analysis, the same CPRR is assumed across these subgroups.

The prior distributions for the RBANS total score variable, within each subgroup are presented in this section. Alternative endpoints analysed using this BCPM will have these prior parameters specified separately. The research participant level random effects are modelled as

$$\gamma_i \sim N(\mu, 12^2), i=1, \dots, k$$

with hyper-priors by sub-group:

$$\mu \sim N(\mu_{sg}, \tau_{sg}^2)$$

where for clinically negative: $\mu_{sg} = 100$, $\tau_{sg} = 2.25$ and for clinically positive: $\mu_{sg} = 88.75$, $\tau_{sg} = 3.75$ (the parameters don't change for ApoE4 status)

 EPAD - 115736	D2.11 Master Statistical Analysis Plan for the EPAD Platform Proof-of-Concept Trial		
	WP2. Statistical/Methodology Engine Room	Version: v2.0 – Final	
	Author(s): [name], [name], [name]	Security: PU	25/36

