18.2. Interim analyses for the DSMB

This section is not finalized.

19. Sample size considerations

The maximum exposure for a research participant to an intervention is 4 years. The time of follow-up (a maximum of 4 years) and maximum number of research participants enrolled to an intervention cohort is defined in the ISA. Complete power calculations and operating characteristics for each intervention will be detailed in the ISA.

A suggestion for a general strategy for power calculations for some generic possible choices of number of subjects, subgroups, and length of follow-up is given in the master protocol.

 EPAD - 115736	D2.11 Master Statistical Analysis Plan for the EPAD Platform Proof-of-Concept Trial		
	WP2. Statistical/Methodology Engine Room	Version: v2.0 – Final	
	Author(s): [name], [name], [name]	Security: PU	32/36

20. Statistical software

Final study reports will be generated using SAS version 9.4 or later. The efficacy models described in this master SAP will be coded in C++ version XXX or later. The ISA will specify further software used for a specific sub trial.

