Annex I. SAS code for simplified frequentist version of primary analysis

The SAS code below covers a simplified frequentist version of the model.

It includes two strata, referenced as 1 and 2 as well as a and b. Time points included are baseline (0) and 6, 12, 18 and 24 months. The dataset should include one record for each visit for each participant. Research participants are identified by rpid.

Parameters α are denoted, for example, as meana6. Parameter μ is denoted mean0. The variance of γ is the parameter s2pt. The parameter σ (the variance of ϵ) is denoted s2e.

```
proc nlmixed data=rbansdata;

parms mean0=100 meana6=-5 meanb6=-2 meana12=-8 meanb12=-3 meana18=-11 meanb18=-4 meana24=-14 meanb24=-5
cprrr=1 s2e=25 s2pt=100;

if (stratum=1) then
change=((time=6)*meana6)+((time=12)*meana12)+((time=18)*meana18)+((time=24)*meana24);

if (stratum=2) then
change=((time=6)*meanb6)+((time=12)*meanb12)+((time=18)*meanb18)+((time=24)*meanb24);

mean=mean0+((treat=0)*change)+((treat=1)*cprrr*change)+pt;

random pt ~ normal(0,s2pt) subject=rpidd;

model rbans ~ normal(mean,s2e);

estimate 'logcprrr ' log(cprrr);

ods output fitstatistics=fit;

ods output parameterestimates=est;

ods output convergencestatus=status;

ods output additional estimates=addest;
```

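### With only a random intercept and independent errors, variation in decline within a stratum makes the CPRR posterior too narrow, mainly in trials with about 24 months of follow-up or more

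*Combined protocol and SAP*

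**What the plan says.** Section 14 of the master SAP lists a "Patient-level random effect" among the features of the Bayesian cognitive progression model. It is a single term per participant, γ_i, the mean score at randomization, with SD fixed at 12. The visit-to-visit changes α and the error SD σ are separate for each of the four strata, while "In the primary analysis, the same CPRR is assumed across these subgroups". Given γ_i, "The errors for the individual observations are modelled as independent normal distributions with a standard deviation of" σ. There is no random slope and no serial correlation.

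The same structure appears in the Annex I code, whose only random term is an intercept. The numbered analyses 1–7 in Section 14 do not relax it. Item 5 adds a calendar-time shift in level, item 6 allows CPRR to differ by stratum, and item 7 lets decline depend on measured covariates. MMRM is named only for the secondary cognitive endpoints (Section 14.1).

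RBANS is assessed every 6 months (Section 5), and "The maximum exposure for a research participant to an intervention is 4 years" (Section 19). LCS visits before baseline also enter the model. Success is P(CPRR < 0.90) > 0.85 and futility is P(CPRR < 0.90) < 0.05 (Sections 14 and 18.1).

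**The concern.** CPRR is a ratio of declines. If participants in one stratum decline at different rates, the later visits of one person move together and the spread grows with time. The model has no term for this, so it counts each further visit as nearly fresh information on the mean decline. The uncertainty of CPRR is then understated, and more so the longer the follow-up.

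Both decision rules are read directly off this posterior. An intervention at the 0.90 boundary would graduate too often and also be dropped too often. The poolability check (Section 14, item 4) uses a 95% credible interval from the same model and would be affected in the same direction; its size was not calculated.

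**Working it through.** The documents state no sample size, power or type I error, so there is no design figure to reproduce. The check compares the standard error that the model reports with the one that applies when slopes vary.

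**Inputs from the documents.** Intercept SD 12; prior log-CPRR ~ N(0, 0.25²); 4 years / 6 months = 8 post-baseline visits. Two values of σ are used. σ = 5 comes from the Annex I starting values "cprrr=1 s2e=25 s2pt=100" (√25). σ = 9 is one reading of the IG(81, 9) prior, whose parameterisation is not stated.

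**Assumptions.** Slope SD ω = 0.5, 1.0 or 1.5 points per 6-month visit; two LCS visits; 150 per arm (3:1 randomization plus shared placebo, taken as 1:1); one look; no dropout; linear control decline of 1 to 3.5 points per visit. The Annex I starting values of −5 and −14 at 24 months correspond to 5/4 = 1.25 and 14/4 = 3.5 per visit; 1 is a lower assumption.

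**Formulas.** With t the visit number (−2 to J), the model's covariance is W = 144·11ᵀ + s²·Id and the true one is V = 144·11ᵀ + σ²·Id + ω²·ttᵀ. The fitted error variance absorbs part of the slope variation: s² = σ² + ω²·Σ(t − t̄)²/(m − 1), with m visits in all. For J = 8, m = 11, t̄ = 3 and the sum is 110, so σ = 5 and ω = 1 give s² = 25 + 110/10 = 36. With X the linearised design (free visit means plus θ = log CPRR) and I = Σ XᵀW⁻¹X, the model SE² is the θ entry of I⁻¹. The true SE² is the θ entry of I⁻¹(Σ XᵀW⁻¹VW⁻¹X)I⁻¹.

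**True SE / model SE** (σ = 9 to σ = 5). The ratio does not depend on total N or on the size of the linear decline.

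| Follow-up | ω = 0.5 | ω = 1.0 | ω = 1.5 |
|---|---|---|---|
| 12 months | 1.01–1.02 | 1.03–1.09 | 1.06–1.17 |
| 24 months | 1.03–1.10 | 1.12–1.31 | 1.23–1.52 |
| 48 months | 1.14–1.37 | 1.45–1.93 | 1.78–2.34 |

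At ω = 0 the ratio is 1.00.

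**Decision probabilities, one case in full** (48 months, σ = 5, ω = 1, decline 1.25, true CPRR 0.90). Model SE 0.0622, true SE 0.1201.

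- Shrinkage w = 0.0625/(0.0625 + 0.0622²) = 0.942; posterior SD = 0.0622·√0.942 = 0.0604.
- Success needs an estimate of θ below (−0.1054 − 1.036·0.0604)/0.942 = −0.178. Probability Φ((−0.178 + 0.1054)/0.1201) = 27%.
- Futility needs an estimate above (−0.1054 + 1.645·0.0604)/0.942 = −0.006. Probability 1 − Φ((−0.006 + 0.1054)/0.1201), about 20–21%.
- With the slope modelled (SE 0.1147), the same steps give 9% and 5%.

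**Range at 48 months, ω = 1.0**, over σ = 5 to 9 and decline 1 to 3.5:

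| | Plan's model | Slope modelled |
|---|---|---|
| Success at CPRR = 0.90 | 17–29% | 6–13% |
| Futility at CPRR = 0.90 | 13–21% | 4–6% |
| Success at CPRR = 1 | 0.1–9% | at most about 1.5% |

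With a negligible prior, a correct posterior would give 1 − 0.85 = 15% success and 5% futility at the boundary.

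**Cross-check by simulation** without the linearisation (4000 trials per scenario, ω = 1.0, 48 months, CPRR = 0.90). At decline 1.25, coverage of the 95% interval is 71% (σ = 5) or 86% (σ = 9), against 97–98% with the slope. Over declines 1.25 and 3.5, success is 25–31% against 16–17%, and futility 9–19% against 1–4%. The levels differ somewhat from the normal approximation, but the direction and the size of the gap agree. Neither calculation includes the negativity restriction on α, the inverse-gamma priors or repeated looks.

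**The case against.** The strongest points on the other side are these.

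- **Decline is not assumed equal for everyone.** Each stratum has its own α and σ. A reader might infer that any variation in decline breaks the model; only variation within a stratum does. This stands.
- **The plan does not say that decline varies.** A reader might take item 7 as an admission that it does. That item only says covariate effects will be examined, as exploratory work.
- **Early looks are little affected.** Interims open when 50 participants have 12 months of follow-up, where the ratio is at most 1.17. In the simulations at 12 months, 95% coverage stayed at or above 99% at decline 1.25 per visit, where the prior dominates, and at about 94–98% at 3.5. Four years is a maximum, and the ISA sets the duration. This stands.
- **The inputs are assumed.** The documents give no slope SD, and σ = 5 is only a starting value. This stands, which is why ranges are shown.
- **The section is declared unfinished, its assumptions in need of justification, and type I error is left to simulation.** The caveat is general and does not name this assumption. No data-generating model is given, and simulating from the same intercept-only model would not reveal the problem.
- **A sensitivity analysis might be enough.** It would help in the final report, but the quarterly stopping decisions are taken from the primary model.

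**Conclusion.** The concern holds for variation in decline within a stratum, and mainly for intervention-specific trials with about 24 months of follow-up or more. At 24 months the understatement of the standard error runs from 3% to 52%, and at 48 months from 14% to 134%, over the assumed slope SDs and the two values of σ. At 48 months and slope SD 1.0, success and futility at the 0.90 boundary both occur well above the rates obtained with the slope modelled.

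A reader might infer that an inactive intervention would often graduate. The documents do not support that as a general statement. At CPRR = 1 the success probability reaches about 9% only with the low decline of 1 point per visit and σ = 5; at 3.5 points per visit it is about 0.1–0.2% for slope SD 1.0. Nor can it be said that a stated error rate is breached, since none is given. If slopes do not vary within strata, there is no error.

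**What to change.** Add a participant-level random slope to the model for interim and final analyses: Y_ij = γ_i + b_i·t_j + the stratum mean curve with CPRR + ε_ij, with (γ_i, b_i) bivariate normal. State the following in the SAP:

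- The intercept SD (now fixed at 12) and the intercept–slope correlation are estimated, with their priors given.
- The prior for the slope SD, checked for early looks, where few visits inform it and the prior will matter.
- Whether b_i is scaled by CPRR in the active arm or added unscaled.

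Keep the intercept-only model as a sensitivity analysis. In the simulations of type I error and operating characteristics, generate data with within-stratum slope variation over a stated range.

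The cost is one more random effect in the code, longer run time, and wider posteriors with lower power where slopes vary. Ineffective interventions would also stop for futility less often at a given look. In the simulation at 48 months, decline 1.25, slope SD 1.0 and CPRR = 1, futility falls from 48% to 14% (σ = 5) or from 28% to 9% (σ = 9). Sample sizes in the ISAs should be set with this in view. Where slopes do not vary, the result is essentially unchanged.

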2. An analysis based on the dataset FAS-Concurrent controls. An analysis based on the dataset FAS-IST controls.
3. An analysis based on the dataset FAS-All controls but only including measurements for $j=0,1,2,\dots$
4. An analysis of different control arms will be conducted in order to check for poolability. This is based on the dataset FAS-Concurrent controls-controls only. All intervention specific controls will be analyzed in a single common run of the BCPM and compared to the control group in the IST: A “treatment effect” CPRR will be fit for each control group (with one intervention chosen to have $CPRR=1$) for the blinded placebo. The posterior mean and 95% credible interval of the ratio of the CPRR between control arms will be presented. If the 95% credible interval for an intervention’s control group does not include 1, this group will be considered to have a different cognitive progression rate.
5. A single instance of the model will be run on the dataset FAS-All controls (each treatment with its own θ_t) with an adjustment for the calendar time of enrolment of the participant in the trial, specific to the strata will be included. The model for the outcome is

$$Y_{ij} = \begin{cases} \gamma_i + \sum_{v=j}^{-1} \alpha_v + \delta_B + \epsilon_{ij} & j = \dots, -2, -1 \\ \gamma_i + \delta_B + \epsilon_{ij} & j = 0 \\ \gamma_i + \exp(\theta_{t_i}) \sum_{v=1}^j \alpha_v + \delta_B + \epsilon_{ij} & j = 1, 2, 3 \dots \end{cases}$$

Where B is an indicator for the “bucket” of time in which a participant was enrolled (specifically the timing of the baseline observation). The indicator B will be based on semi-annual buckets starting and working backwards from the last participant enrolled. The following modelling of the time effects will be used.

$$\delta_B \sim N(\delta_{B-1}, \tau^2), B=S^*, \dots, N_B$$

 EPAD - 115736	D2.11 Master Statistical Analysis Plan for the EPAD Platform Proof-of-Concept Trial		
	WP2. Statistical/Methodology Engine Room	Version: v2.0 – Final	
	Author(s): [name], [name], [name]	Security: PU	27/36

Where S^* is defined as the first 6-month period prior to an intervention starting enrolment in the trial, with the number of 6-month buckets, N_B , a function of the calendar time enrolling the participant. The parameter is modelled as

$$\tau^2 \sim IG(0.01, 0.01).$$

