An additional analysis will be conducted where there is a different vector of the δ , where the δ are separate for the clinically +ve and clinically –ve strata.

6. An analysis of the model will be conducted where the CPRR will be separate by each individual strata.
7. The effect of covariates will be examined. As the RBANS values are normalized, the focus will be on models, where the covariates influence the change over time. As the actual covariate will typically be assessed at baseline, this will only use data at and after baseline. Analyses of the BCPM with standardized covariates Z_1, \dots, Z_C will be conducted by the following model

$$Y_{ij} = \begin{cases} \gamma_i + \epsilon_{ij} & j = 0 \\ \gamma_i + \exp\left(\theta_{t_i} + \sum_{c=1}^C \beta_c Z_{ic}\right) \sum_{v=1}^j \alpha_v + \epsilon_{ij} & j = 1, 2, 3 \dots \end{cases}$$

Where the prior distribution of the coefficients for each covariate will be

$$\beta_c \sim N(0, 10^2), c = 1, \dots, C$$

Each continuous covariate will be standardized by the patient-weighted mean and standard deviation for each covariate. Indicator variables will be left as 0/1 variables.

Exploratory analyses will be conducted on an array of covariates.

Subset analyses and additional analyses for each intervention will be specified in the intervention specific SAP.

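### The calendar-time model in item 5 corrects drift in the level of RBANS but not drift in the rate of decline, so it can agree with a biased all-controls CPRR

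*Combined protocol and SAP*

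**What the plan says.** SAP Section 14, item 5, runs one model on FAS-All controls "with an adjustment for the calendar time of enrolment of the participant in the trial, specific to the strata will be included". The bucket B is a half-year of enrolment, "specifically the timing of the baseline observation", so each participant has exactly one bucket. In the displayed model δ_B is added to all three lines: LCS visits, baseline and post-baseline visits. It stands outside the product of exp(θ) and the summed visit effects α, and the α carry no calendar index. The buckets are linked by a random walk. A further version is planned "where the δ are separate for the clinically +ve and clinically –ve strata".

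The target is the CPRR, which "represents the multiplicative change to the mean decline of a research participant on a control or placebo treatment". The participant effect is a random intercept with standard deviation 12 around a subgroup mean.

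Section 14 makes FAS-All controls the primary set, whereas Section 8 names FAS-concurrent controls. Section 14 also lists analyses on FAS-Concurrent and FAS-IST controls (item 2), a poolability check on concurrent placebo (item 4) and a covariate model (item 7). It describes itself as not completely final.

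**The concern.** Placebo participants enrolled in earlier years may differ from current ones in two ways: where they start, and how fast they decline. CPRR is a ratio of declines. If older placebo declined faster, pooling makes the control decline too steep, and an inert drug looks as if it slows progression. A reader would expect the calendar-time analysis to reveal this. As written it adjusts only the starting level, so under rate drift it would nearly reproduce the unadjusted all-controls estimate, and the agreement could be taken as confirmation.

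The plan's other models work on the rate. Item 4 compares placebo groups through a CPRR, and item 7 puts covariates inside the exponent because RBANS is already normalised. Item 4 is limited to concurrent controls, and item 7 does not name calendar time.

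**Working it through.** **Algebra.** For j ≥ 1, E(Y_ij − Y_i0) = [γ_i + exp(θ)Σα + δ_B] − [γ_i + δ_B] = exp(θ)Σα. The bucket term is gone. Splitting δ by clinical status changes nothing in this line.

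**Inputs.** The SAP gives no sample size or operating characteristics (Section 19 leaves them to the ISA), so there is no figure of its own to reproduce.
- From Section 14: intercept variance 12² = 144; prior θ ~ N(0, 0.25²); success if P(CPRR < 0.90) > 0.85.
- From the Annex I starting values, used only as scenarios: changes at 6, 12, 18 and 24 months of −5, −8, −11, −14 (stratum a) and −2, −3, −4, −5 (stratum b); error variance 25, with 9 and 81 also tried.
- Assumed: 150 active and 50 own placebo (3:1), 150 older placebo in one earlier bucket, 0 or 2 LCS visits, true CPRR 1, and δ_B estimated freely rather than smoothed.

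**Method.** The mean model is fitted by generalised least squares to expected data, which gives large-sample estimates of CPRR.

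**Hand check.** With older placebo declining 25% faster, the pooled placebo decline is (50 × 1 + 150 × 1.25)/200 = 1.1875 times the current one, and 1/1.1875 = 0.842.

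**Results** (ranges over both strata and error variances 9 to 81):

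| Scenario | No δ_B | δ_B as in item 5 | δ_B plus free rate term |
|---|---|---|---|
| Older placebo declines 25% faster, no LCS visits | 0.842 | 0.844–0.858 | 1.000 |
| Same, two LCS visits, faster decline there too | 0.778–0.792 | 0.777–0.790 | 1.000 |
| Older placebo 3 points lower, same decline, 0 or 2 LCS visits | 0.841–0.996 | 1.000 | 1.000 |

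**Success rule under rate drift.** At error variance 25 with the prior, P = Φ[(ln 0.90 − θ̂)/SE].
- Two LCS visits with the drift there too: 1.00 in stratum a and 0.88 in stratum b, with or without δ_B. For b: (−0.1054 − ln 0.806)/0.093 = 1.19, giving 0.88.
- No LCS visits: stratum a 0.92 without δ_B and 0.89 with it, from (−0.1054 − ln 0.852)/0.045 = 1.22. Stratum b 0.61 and 0.59, from (−0.1054 − ln 0.877)/0.114 = 0.23.

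The inert drug passes 0.85 in three of these four cases. δ_B moves the probability by 0.03 or less in each.

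**Price of the rate term.** With error variance 25, two LCS visits, no drift and the prior on θ, the SE of log-CPRR rises from 0.038 to 0.056 (a, 0.056/0.038 = 1.47) and from 0.097 to 0.134 (b, 1.38) when the multiplier acts on j ≥ 1. If it also acts on the LCS visits, the SEs are 0.052 (1.37) and 0.126 (1.30). The largest rise seen is 0.028 to 0.045 (1.61): stratum a, error variance 9, no LCS visits, rate drift, no prior on θ.

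**Effect of a prior on the multiplier.** At error variance 25 without LCS visits and without the prior on θ, a N(0, SD²) prior on the older bucket's log multiplier gives CPRR 0.987 (a) and 0.938 (b) for SD 0.25, and 0.946 and 0.878 for SD 0.1.

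**The case against.** A reader might infer that δ_B does nothing because the participant intercept already absorbs it, so that only rate drift can bias CPRR. The model does not support that. The intercept is a random effect, "\gamma_i \sim N(\mu, 12^2), i=1, \dots, k", shrunk towards a subgroup mean, so an unmodelled level shift leaks into CPRR. The third row of the table shows the leak, and shows that δ_B removes it. δ_B is useful but incomplete.

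A reader might also infer that item 5 is the plan's only protection against older controls. It is not. Item 2 includes FAS-Concurrent controls and FAS-IST controls, and the latter is a purely randomised comparison that this drift cannot reach. If Section 8 governs, non-concurrent placebo does not enter the primary result at all. A gap between the control sets could expose the drift. These points stand and lower the severity. But the smaller sets are less precise, and the SAP states no rule for what follows if they disagree.

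Third, the success probabilities depend on chosen drift, arm sizes and variances, and stratum b without LCS visits stays below 0.85. They illustrate the mechanism and are not operating characteristics of this plan.

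**Conclusion.** The point holds. By the plan's own formula, item 5 and its clinical-status variant correct level drift and leave rate drift untouched. Under an assumed 25% faster decline in older placebo, CPRR is 0.84 without the adjustment and 0.84 to 0.86 with it, against a true value of 1. That the bucket term cancels from changes needs no assumption. The size depends on the assumed drift, the share of older placebo and the Annex I scenario values.

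This should be fixed, but it is not critical: item 5 is supplementary, the success rule attaches to the primary analysis, and other control sets are analysed. It matters more if FAS-All controls is the primary set, so the conflict between Sections 8 and 14 should be settled at the same time.

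**What to change.** Keep δ_B and add a bucket term on the rate. For j ≥ 1, the mean becomes γ_i + exp(θ_t + φ_B)Σα_v + δ_B, with φ = 0 in the latest bucket and a random walk backwards from it. Give φ its own innovation prior on the log scale; the IG(0.01, 0.01) prior was set for shifts in RBANS points. Do the same in the version split by clinical status, and report φ_B beside CPRR.

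δ_B must stay. With a 3-point level drift, error variance 25 and no LCS visits, a rate term alone with log-scale SD 0.1 to 0.25 leaves CPRR at 0.948 to 0.973 in stratum b.

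The innovation prior needs thought. A tight one removes only part of the bias. With a free multiplier on j ≥ 1, the analysis is no more precise than FAS-IST controls (SE 0.056 and 0.134 for both, two LCS visits). State the prior and show a second value as sensitivity.

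Cost: a few lines of code and SAP text, and a standard error of log-CPRR about 30 to 60% larger in this one analysis. The primary analysis is unchanged.

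### The item 7 covariate model has no term for RBANS level, so a covariate related to level gets a biased progression coefficient; the exploratory covariate results are affected, the CPRR decision rules are not

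*Combined protocol and SAP*

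**What the plan says.** Item 7 of Section 14 gives the reason for its model form as "As the RBANS values are normalized, the focus will be on models, where the covariates influence the change over time". It then restricts the data: "As the actual covariate will typically be assessed at baseline, this will only use data at and after baseline". In the displayed model the baseline line is γ_i plus error. The later visits are γ_i plus exp(θ + Σβ_c Z_ic) times the cumulative mean change, plus error. The covariates Z appear nowhere else. The coefficients have the prior "\beta_c \sim N(0, 10^2), c = 1, \dots, C". The item adds: "Exploratory analyses will be conducted on an array of covariates".

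Earlier in Section 14 the γ_i "parameters are the random effects specific to a research participant" are defined as the participant's own mean score at randomization. They have the distribution "\gamma_i \sim N(\mu, 12^2), i=1, \dots, k". The mean μ has a hyper-prior by sub-group, centred at 100 for clinically negative and 88.75 for clinically positive participants. It has no covariate term.

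Section 14.1 says that the secondary cognitive endpoints need changes to the model because they are not normalised by sex and age. By implication, sex and age are what the RBANS normalisation covers.

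**The concern.** Together, the item 7 equation and the distribution of γ_i say that, within a stratum, every covariate is independent of RBANS level. That is doubtful for any baseline measure of disease severity, and removing the effects of sex and age does not make it true.

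If the assumption fails, the random intercept repairs the fit only in part. It is a shrunken effect, pulled towards a mean that ignores Z. Where participants with a given value of Z sit lower at every visit, their intercepts are drawn upwards. The low follow-up scores that remain can be fitted only through β, the one place where Z appears, and the model then shows faster decline where there is only a lower level. The N(0, 10²) prior on β is wide on the log-rate scale and does little to shrink this.

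At stake is the reading of the covariate results: a marker of level could be described as a marker of progression rate. The chance of this grows with sample size and with the number of covariates tried.

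**Working it through.** The SAP gives no sample size, error rate or effect size for item 7, so there is no figure of its own to reproduce.

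**Inputs**
- Intercept variance 144 (Section 14).
- Cumulative placebo decline A at 0, 6, 12, 18 and 24 months: steep stratum (0, −5, −8, −11, −14), mild stratum (0, −2, −3, −4, −5). These are starting values in the Annex I code, used as illustrations.
- Residual variance s²: assumed 25 to 81 (SD 5 to 9). The lower end is the Annex I starting value; the parametrisation of the IG(81, 9) prior is not defined.
- Correlation r of a standardised covariate with RBANS level: assumed 0.1, 0.3 and 0.5. Level shift per SD of Z: b = 12r.
- N = 200 (assumed), with 3 or 5 visits. True β = 0.

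**Linearised (GLS) bias**

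Let n be the number of visits, S = ΣA, Q = ΣA² and V = s²I + 144J. Then

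bias(β) = b · (A′V⁻¹1)/(A′V⁻¹A)

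A′V⁻¹1 = S/(s² + 144n)

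A′V⁻¹A = [Q − 144S²/(s² + 144n)]/s²

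Without γ_i the bias would be b·S/Q. The standard error of β is 1/√(N·A′V⁻¹A).

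**Worked case: steep stratum, 5 visits, s² = 25, r = 0.3**
- S = −38, Q = 406, s² + 144n = 745.
- A′V⁻¹1 = −38/745 = −0.0510.
- A′V⁻¹A = (406 − 144·1444/745)/25 = 5.08.
- Bias per RBANS point = −0.0510/5.08 = −0.0100. Without γ_i it would be −38/406 = −0.0936, so 11% remains.
- b = 3.6, so β is biased by −0.036 and exp(β) = 0.964 per SD.
- SE = 1/√(200·5.08) = 0.031, so bias/SE = 1.15. The chance that the 95% interval excludes zero is Φ(1.15 − 1.96) ≈ 21%.

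**Across the assumed range**

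The share of the bias left after γ_i is 11% (residual SD 5) to 28–29% (SD 9) with 5 visits, and 14% to 34% with 3 visits. So γ_i absorbs roughly 65–90%.

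| r | spurious exp(β) per SD, 5 visits | 95% interval excludes 0, N = 200 | same, N = 400 |
|---|---|---|---|
| 0.1 | 0.91–0.99 | 7–9% | 8–14% |
| 0.3 | 0.76–0.96 | 21–46% | 37–74% |
| 0.5 | 0.64–0.94 | 48–87% | 78–99% |

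**Simulation check**

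The non-linear model was fitted by likelihood with N = 200, 3:1 allocation, true CPRR 0.75, true β = 0, intercept SD fixed at 12, known residual variance and 400 replicates per setting.

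| r | item 7 model, false signal |
|---|---|
| 0 | 5.5–6.5% |
| 0.1 | 8.5–9% |
| 0.3 | 22–42% |
| 0.5 | 48–85% |

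With Z also in the mean of γ_i, the rate was about 4–8% in every setting and the mean β lay between −0.003 and 0.006. The estimated CPRR stayed at 0.75–0.76 under the item 7 model.

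**Limits**

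The simulation used flat priors rather than the SAP's priors. It covers the steep stratum at both residual SDs and the mild stratum at SD 5. The mild stratum at SD 9 rests on the formula alone, because the fit became singular there.

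**The case against.** **γ_i already carries level.** This is largely right. A reader might infer that any covariate related to baseline RBANS will be reported as altering progression. The calculation does not support that: most of the level effect is absorbed, a weakly related covariate is flagged little more often than 5%, and at r = 0.3 and N = 200 fewer than half of trials show a false signal. The item also sets no interval criterion or other decision rule for β, so the 95% criterion used here is only a yardstick.

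**The analysis is exploratory.** This also stands. A reader might infer harm to the efficacy conclusion, or to later enrichment or restrictions on shared placebo. The success and futility rules use the CPRR from the model without covariates, and the documents do not link item 7 results to enrichment or to the choice of controls. Item 7 names no covariates either, so any candidate is a guess.

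**The sub-group means of 100 and 88.75 are already modelled.** Correct. They show that normalised scores still vary with disease status, but the gap between strata is handled by μ. Only level differences within a stratum matter here, and the documents give no figure for those.

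**The inputs are not planning values.** True. Annex I describes a simplified frequentist model, and its starting values ("cprrr=1 s2e=25 s2pt=100") include an intercept variance of 100 rather than 144. The size depends strongly on residual variance. If IG(81, 9) means shape and scale, its prior mean is 9/80 ≈ 0.11, and leakage would be negligible were the true variance that small. If the true variance were 25, the data would largely override that prior. An approximate conjugate update gives (9 + 1200·25/2)/(81 + 600 − 1) ≈ 22 for 300 participants with 5 visits, and (9 + 400·25/2)/(81 + 200 − 1) ≈ 18 for 200 participants with 3 visits.

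**The section is declared unfinished and speaks only of a focus.** Section 14 does say that its assumptions need justification, and the word does not rule out level models. But this assumption is not identified, and the only equation written has no level term. The document is published for reuse, so the equation may be taken over as it stands.

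**Conclusion.** The point holds as a bias in an exploratory analysis. Followed as written, item 7 gives a biased β for a covariate related to RBANS level within a stratum, and normalisation for sex and age does not justify leaving level out. The direction of the bias and its removal by a level term follow from the model. Its size rests on the assumed declines, residual SD, correlation and N: close to nominal error for weak correlation, and a false signal in roughly a fifth to just under a half of trials at r = 0.3 with 200 participants. False signals become near certain only when strong correlation, large residual SD and large N coincide. There is no support for reading this as a flaw in the CPRR or in the 0.85 and 0.05 rules.

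**What to change.** In item 7, let the mean of the random effect depend on the covariates: γ_i ~ N(μ + Σλ_c Z_ic, 12²), with a weak prior on λ_c on the RBANS scale, for example N(0, 10²). The displayed equations for Y and the definition of γ_i as the participant's own level at randomization can then stay as they are. Remove normalisation as the reason for modelling change only, and report λ_c beside β_c so that effects on level and on rate can be told apart.

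The cost is one extra parameter per covariate and slightly wider intervals for β. In the simulation, for example, the SD of β rose from 0.066 to 0.075 (steep stratum, residual SD 9, r = 0.3).
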